	
will be stored for future testing of additional parameters in the research fields of acute decompensated heart failure and acute kidney injury.
 
Furthermore, the available laboratory values from routine clinical practice (see Table 1) will be entered in the Case Report Form (eCRF).
 
On days 1-5, the patient will be asked to complete a Patient Symptom Assessment Sheet (see Annex D).
 
On days 1 and 3, the treating physician will be asked to complete a very brief survey (Annex E) to provide a qualitative assessment of the patient's perceived intravascular volume status and renal function. The study physician will conduct a non-invasive clinical assessment of the patient (including e. g. body weight, height, edema grade, blood pressure, heart rate, respiratory rate, jugular venous distension assessment, oxygen saturation) on days 1-5.
 
In addition, the study physician will record in the eCRF detailed information regarding diuretics dosage, i. v. fluid application, and requirement of renal replacement therapy as ordered by the clinicians in the hospital.
 
Laboratory values and assessments (see Table 1) will be captured on each day that the VFI is administered and these data will be entered into the eCRF. Any AEs determined by the investigator to be related or possibly related to the VFI will be captured. Patients will also receive a follow up phone call 7 days (<math>\pm 2</math> days) after the second dose of VFI was administered, and a second follow up call 30 days after the second dose of VFI was administered. This second phone call will serve as the end-of-study (EOS) follow-up call. Any AEs determined by the investigator to be related or possibly related to the VFI will be captured during the follow up calls and will be followed to resolution. Additionally, in-person follow up visits may be scheduled, as determined by the investigator. During day 1-5, during follow-up phone calls or study visits and through information accessed within the hospital computer system or obtained from treating physicians or relatives, the following study outcomes will be recorded: mortality, length of hospital stay, readmission for heart failure, episodes of acute kidney injury, requirement of fluid resuscitation, episodes of symptomatic hypotension, successful reduction of body weight.
 
Upon conclusion of the study, the recorded clinical data will be provided to an independent data adjudication committee (DAC) in a pseudonymized fashion. The DAC will be asked to

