### 4.3 Secondary variables

#### 4.3.1 Efficacy

- Estimated PV (by Kaplan-Hakim's formula, see chapter 7.2) and measured PV (assessed by FAST methodology) on days 1 and 3
- Estimated TBV (by Nadler's formula, see chapter 7.2) and measured TBV (mTBV: calculated from mPV and measured hematocrit, see chapter 7.2) on days 1 and 3
- Estimated GFR (CKD-EPI formula, sMDRD, Cystatin C formula, and Creatinine-Cystatin C formula, see chapter 7.2) and measured GFR (assessed by FAST methodology) on days 1 and 3 in heart failure patients undergoing active fluid management
- Development of AKI within 72 hours after day 1 and 48 hours after day 3 respectively
- Current level and level within last 24 hours of well-being, dyspnea, dizziness, nausea reported on day 1 and day 3
- Subjectively reported symptoms (PGA, dyspnea, dizziness, nausea) determined using patient symptom assessment sheets within the following 24 and 48 hours on day 1 and following 24 and 48 hours on day 3
- Low-output complications within the next 24 and 48 hours (e. g. subjectively reported dizziness/nausea, PGA, hypotension (Systolic <100, diastolic <60mmHg), need for iv-fluid therapy) at day 1 and within the next 24 and 48 hours at day 3
- Risk of being refractory to diuretic therapy (e. g. require dosage increases of furosemide/torsemide, require ultrafiltration/RRT within the next 24-48 hours, fail to improve subjectively in PGA and dyspnea scales) within 24 and 48 hours on day 1 and day 3

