## **7 Statistical analyses / methods**

### **7.1 General remarks**

The primary objective is to assess the safety and function of the FAST PV and mGFR Technology in hospitalized patients with heart failure. This is a phase II trial. No formal hypothesis test is performed to assess the primary objective. This is justified as follows: 1. Both function and safety cannot be uniquely assessed by one specific endpoint, but there exist several relevant endpoints and endpoint-related criteria which must be investigated in order to assess the global function and safety. 2. For reasons of feasibility, the studies sample size is limited to 50 patients which is an adequate number in the context of a phase II trial. However, this limited number does not allow to address a complex multiple testing problem with adequate power.

Therefore, all analyses including p values are purely descriptive. The aim is to generate new hypotheses to be tested in subsequent phase III trials.

For continuous variables descriptive statistics include mean, standard deviation, median, inter quartile range and range. For categorical variables descriptive statistics include absolute and relative frequencies.

Due to the low number of patients in one of the centers, no adjustment for center will be done in the analyses.

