To evaluate whether eGFR calculation by the CKD-EPI formula and sMDRD formula on days 1 and 3 provides an accurate estimate of measured GFR (mGFR; assessed by FAST methodology) in heart failure patients undergoing active fluid management, linear regression models with the measured value at a given day as dependent variable and the estimated version as independent variable will be generated. The models will be adjusted for mPV and mPVS. Further, Bland-Altman plots will be generated comparing the estimated and measured parameters separately for day 1 and day 3. The defined limits of agreements are  $\pm 6\text{ml/min}$ . Diagnostic accuracy including frequencies of values between 15% and 30% of the measured value will be determined as mentioned before.

To evaluate whether patients with a low mGFR/eGFR ratio on days 1 and 3 are at higher risk of developing AKI within the following 72 (day 1) and 48 (day 3) hours, logistic regression models with the AKI status as dependent variable and mGFR/eGFR ratio as independent variables will be generated. The models will be adjusted for mPVS, mTBVS. Three different versions of the mGFR/eGRF ratio will be evaluated: ratio  $< 1$ ; ratio  $<$  first quartile; ratio as continuous parameter.

To evaluate whether ranges of mPVS (low mPVS ( $< -10\%$ ), normal mPVS ( $-10$  to  $+10\%$ ), high mPVS ( $> +10\%$ )) and/or mTBVS (low mTBVS ( $< -10\%$ ), normal mTBVS ( $-10$  to  $+10\%$ ), high mTBVS ( $> +10\%$ )) on days 1 and 3 are associated with subjectively reported symptoms (current PGA  $> 15$ , current dyspnea  $> 15$ , current dizziness  $> 15$ , current nausea  $> 15$ ) determined using patient symptom assessment sheets within the following 24-48 hours, a logistic regression

---

model with occurrence of symptoms (PGA, dyspnea, dizziness, nausea) as dependent variable and the categorized measured value (mPVS, mTBVS) as independent variables will be generated. The models will be adjusted for mean arterial pressure.

To evaluate whether patients with low mPVS ( $< -10\%$ ) or low mTBVS ( $< -10\%$ ) on day 1 or on day 3 are at risk of developing low-output complications within the next 24-48 hours (subjectively reported dizziness  $> 15$ , nausea  $> 15$ , PGA  $< 25$ , hypotension (Systolic  $< 100$ , diastolic  $< 60$  mmHg), need for iv-fluid therapy), logistic regression models using mPVS and mTBVS as independent variables will be used.

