To evaluate whether patients with a high mPVS ( $> +10\%$ ) or a high mTBVS ( $> +10\%$ ) on day 1 and/or day 3 are at risk of being refractory to diuretic therapy (defined as any dosage increases of furosemide i.v. dose equivalent, adding thiazide after day 1, require ultrafiltration/RRT within the next 24-48 hours, fail to improve subjectively in PGA and dyspnea scales, fail of mean weight loss during the study period Day 1-Day 5 of at least 0,5 kg/d) logistic regression models using mPV and mTBV as independent variables will be used.

To evaluate whether the changes of ePV (using relative and absolute change as well as the Strauss' formula) and eTBV (using relative and absolute change) from day 1 to day 3 adequately reflects the changes of mPV and mTBV Bland-Altman plots will be generated. These plots will be analysed exploratory, since no appropriate values for limits of agreements are available. The amount of values within 10% and within 30% of the measured values will also be determined. In addition, the diagnostic test accuracy including 95% confidence interval as proposed by Obuchowski will be calculated.

To evaluate whether the change of mPV and mTBV and changes of mPVS and mTBVS from day 1 to day 3 as well as the mPVS and mTBVS on Day 1 and Day 3 is predictive of the remaining length of stay at the given day (i.e. remaining length of stay starting with day 1 or with day 3), dialysis/ultrafiltration requirement, or rehospitalization within 30 days, or mortality, linear (remaining length of stay), logistic (dialysis/ultrafiltration, rehospitalization within 30 days) or Cox-regression models (mortality) will be utilized using changes of mPV and mTBV from day 1 to day 3 (first model), changes of mPVS and mTBVS from day 1 to day 3 (second model), and mPVS and mTBVS at day 1 (third model) and day 3 (fourth model) as independent variables.

To evaluate whether the percentage changes of mGFR from day 1 to day 3 ( $< 0$  vs.  $\geq 0$ ; continuous) predicts the percentage changes of eGFR from day 2 to day 4 (CKD-EPI formula only;  $< 0$  vs.  $\geq 0$ ; continuous), a logistic as well as a linear regression model will be used.

The same will be done to investigate the changes in eGFR from day 1 to day 3 (all formulas) as the dependent variable. Further, exploratory Bland-Altman plots without predefined limits of agreement will be created.

To evaluate whether patients with a high PVS or TBVS on Day 1 ( $> +10\%$ ) and a decreasing PVS

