## 8 Changes from the protocol

In general, no variable selection will be done in the regression models due to limited sample size. Rather clinical expertise regarding the most important explanatory variables will be used to determine a fixed, hierarchical set of possible covariates.

The mPVS and mTBVS are used to determine patients with low, normal or high PV and TBV and thus, the status will be defined based on established estimation formulas for ideal PV and TBV incorporating weight and/or height.

The analysis of the time course of estimated and measured PV and TBV via t-tests was replaced by Bland-Altman-analyses since these analysis better reflects the underlying question of clinically equivalent measurements. Further, the curve characteristics (e.g. times when maximal and minimal volumes are reached and the areas under the curve) based on only few time points were deemed to be of minor meaningfulness.

Haemoglobin for estimating plasma volume changes by Strauss formula and cystatin C values to estimate Glomerular Filtration Rate were also recorded during the study and will also be utilized for the analysis in the respective estimation formulas.

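### SAP 7.7.1 counts PGA events in opposite directions (above 15 as a symptom, below 25 as a low-output complication), so one of the two models treats the well end of the scale as the event

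*SAP*

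**What the plan says.** SAP 7.7.1 turns the patient global assessment into a yes/no outcome twice, in consecutive paragraphs.

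- **Symptom model.** The events are "current PGA $> 15$ , current dyspnea $> 15$ , current dizziness $> 15$ , current nausea $> 15". Their occurrence is the dependent variable of a logistic regression on categorised mPVS and mTBVS, adjusted for mean arterial pressure.
- **Low-output model.** Dizziness stays at above 15, and the list continues "nausea $> 15$ , PGA $< 25$ , hypotension". These are called complications, and they are regressed on mPVS and mTBVS with no stated adjustment.

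A third use follows in the diuretic-refractoriness definition, which includes patients who "fail to improve subjectively in PGA and dyspnea scales", with no statement of which way improvement runs.

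SAP 4.3.1 describes what the sheet records: "Current level and level within last 24 hours of well-being, dyspnea, dizziness, nausea reported on day 1 and day 3". It gives no PGA cut-off or direction. Nor do the secondary objectives in Protocol 4.2 and section 14, and neither abbreviation list defines PGA. The sheet itself (Protocol Annex D) is not in the text available for this review. That is not a fault of the plan.

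**The concern.** Dizziness and nausea keep the same sign in both lists, and only the PGA flips. The cut-off also moves, from 15 to 25, so correcting one inequality sign would not make the definitions match.

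Both outcomes are meant to be bad for the patient. If high PGA means worse, the low-output model counts the best scores as complications. If high PGA means better, the symptom model counts the best scores as symptoms. A programmer following the SAP literally would misclassify the PGA outcome in one of the two analyses.

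The consequence depends on a choice the SAP leaves open.

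- **PGA analysed as its own component:** its association with volume status would tend to appear with opposite signs in the two analyses.
- **Components pooled into an any-component outcome:** every patient with a PGA of 15 or less is a low-output event, whatever the blood pressure or fluid need. Every low-output non-event has a PGA of 25 or more, and so is a PGA symptom event when the same item is read at the same assessment.

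**Working it through.** **Inputs.** Rule A: PGA > 15 (SAP 7.7.1, symptoms). Rule B: PGA < 25 (SAP 7.7.1, low-output complications). The plan states no figure that depends on these rules, so there is none to reproduce. The steps assume that both rules are applied to the same PGA item.

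**Step 1: coverage of the scale.** A score of 15 or less fails A but meets B. A score of 25 or more fails B but meets A. A score strictly between 15 and 25 meets both. No score fails both. The scale range is not given, so three integer scales were assumed:

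| Assumed scale | Scores | Meet A | Meet B | Meet both | Meet neither |
|---|---|---|---|---|---|
| 0–30 | 31 | 15 | 25 | 9 (16 to 24) | 0 |
| 0–50 | 51 | 35 | 25 | 9 (16 to 24) | 0 |
| 0–100 | 101 | 85 | 25 | 9 (16 to 24) | 0 |

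On each scale the lowest score is an event only under B and the highest only under A. Whichever end is the well end, exactly one rule counts it. (On a 0–20 scale every score would meet B.)

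**Step 2: event rates.** Let q be the share of patients scoring strictly between 15 and 25. Since P(A or B) = 1,

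P(A) + P(B) = 1 + q.

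The sum is at least 1, so at least one rate is 50% or more. With 50 scores of which 20 exceed 15, the other 30 are 15 or below and all meet B, giving at least 30 low-output PGA events. Taking either rule as the reference, every non-event is an event under the other, so specificity is 0%. No distribution is assumed here.

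**Step 3: direction of association, PGA analysed alone.** For a contrast between two volume groups,

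difference in P(B) = −(difference in P(A)) + (difference in q).

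The two contrasts have opposite signs whenever the difference in q is smaller in absolute size than the difference in P(A). With q = 0 in both groups, B is the complement of A and the crude odds ratios are exact reciprocals: 2.0 under A gives 1/2.0 = 0.50 under B.

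**Step 4: illustration with assumed shares.** Fix the crude odds ratio for A at 2.0 and let q be equal in both groups. The table gives the odds ratio for B:

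| P(A), comparison group | q = 0 | q = 0.10 | q = 0.20 |
|---|---|---|---|
| 0.30 | 0.50 | 0.44 | 0.31 |
| 0.50 | 0.50 | 0.51 | 0.49 |
| 0.70 | 0.50 | 0.57 | 0.60 |

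One cell in full: P(A) = 0.50 becomes 0.667 at an odds ratio of 2.0. With q = 0.20, P(B) = 1.20 − 0.50 = 0.70 in the comparison group and 1.20 − 0.667 = 0.533 in the other. The odds ratio is (0.533/0.467)/(0.70/0.30) = 0.49.

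**Step 5: limit.** Reversal is not certain. With P(A) of 0.50 versus 0.667 and q of 0 versus 0.20, P(B) is 0.50 versus 0.533 and the odds ratio is 1.14.

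**The case against.** Four points can be made for the plan.

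1. **The sheet is not visible.** Treating PGA as the well-being level of SAP 4.3.1 is an inference. Only the symptom rule says current, so the low-output rule might use the last-24-hours level. The event-rate identity therefore needs the same-item assumption. However, a different recall window would not by itself reverse a scale, and nothing in either document says the two items are scored in opposite directions.

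2. **Reversed coding can be undone.** If PGA is fitted alone, flipping a binary outcome only inverts the odds ratio. That is right for a pure flip, but the cut-offs also differ, the reader would need a scale direction that the SAP does not give, and the SAP does not say whether components are pooled. If they are, the error cannot be undone from the reported result. The planned models also differ in covariates, so the crude reciprocals above would not appear exactly in the outputs.

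3. **SAP section 8 need not mention it.** That section lists departures from the protocol, starting with "In general, no variable selection will be done in the regression models due to limited sample size". The protocol sets no PGA cut-off, so silence there breaches nothing. This stands: section 8 simply offers no explanation.

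4. **Little weight.** SAP 7.1 says "all analyses including p values are purely descriptive", and the data review in SAP section 6 may document changes before analysis. This limits the severity. But SAP 7.1 also gives the aim as generating hypotheses for phase III, and a reversed outcome can generate a wrong one.

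**Conclusion.** The contradiction holds as written. On any one-directional scale extending below 15 and above 25, one of the two PGA rules in SAP 7.7.1 counts patients at the well end as events. The documents do not settle which one. The word well-being in SAP 4.3.1 hints that high may mean better, but does not state it.

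If the same item is used, the two event rates sum to 1 + q, at least one is 50% or more, and no score is a non-event under both. A reversed association is likely but not guaranteed: in the illustration an odds ratio of 2.0 becomes 0.31 to 0.60, under assumed shares only.

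The damage is confined to one component of two secondary descriptive analyses. Safety and FD003 stability are untouched. It should be fixed before analysis.

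**What to change.** In the SAP, before analysis:

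- State the PGA range and direction once, taken from the symptom sheet.
- Reconcile the two rules in 7.7.1 so that both count the worse end as the event. If the cut-offs are meant to differ, give the reason. No cut-off is proposed here.
- Say for each rule whether it uses the current or the last-24-hours item.
- Say whether the components are analysed separately or pooled.
- Apply the same direction to failure to improve in PGA in the diuretic-refractoriness definition. That wording is not contradictory, but it cannot be coded until the direction is stated.

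The cost is SAP wording only. The sheets are already planned daily (Protocol Synopsis: "On days 1-5, the patient will be asked to complete a" symptom sheet), so no new data, visits or model terms are needed.

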### **Size Estimation**

We plan to enrol 50 eligible patients. Due to the explorative nature of this phase II study a formal sample size calculation is not possible. However, the sample size of 50 patients is sufficient to guarantee reasonable accuracy with respect to the main objectives of the trial as specified below.

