### **Secondary objectives:**

- To evaluate how estimated PV (ePV) and estimated total blood volume (TBV) assessments on days 1 and 3 (by established measures such as Nadler's formula or Metropolitan Life Tables) predict measured PV (mPV; as assessed by FAST methodology) and measured TBV (mTBV; calculated from mPV and measured hematocrit) at these time points. Simple linear regression models will be generated and potentially adjusted for relevant confounders.
- To evaluate how a clinical evaluation (including a reasonable subset of the variables age, gender, BMI, hematocrit, edema grade, presence of pulmonary rales, presence of jugular venous congestion, arterial blood pressure, NYHA stage, respiratory rate) on days 1 and 3 predicts mPV and mTBV at these time points. Optimal linear models will be chosen by comparing the results of different variable selection models for the corresponding linear model (backward selection based on p-Values and Akaike Information Criterion, best subset selection etc.).
- To evaluate whether eGFR calculation by the CKD-EPI formula on days 1 and 3 provides an accurate estimate of measured GFR (mGFR; by assessed by FAST

methodology) in heart failure patients undergoing active fluid management. Simple linear regression models will be generated and potentially adjusted for relevant confounders.

- To evaluate whether patients with a low mGFR/eGFR ratio on days 1 and 3 are at higher risk of developing AKI within the following 48-72 hours. Logistic regression models will be generated and potentially adjusted for other relevant confounders.
- To evaluate whether ranges of mPV (low mPV, normal mPV, high mPV) and/or mTBV (low mTBV, normal mTBV, high mTBV) on days 1 and 3 are associated with subjectively reported symptoms (PGA, dyspnea, dizziness, nausea) determined using patient symptom assessment sheets within the following 24-48 hours. Logistic regression models will be generated and potentially adjusted for other relevant confounders. Associations will be assessed by chi-square interaction tests and by Spearman's correlation coefficient.

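### For the volume–symptom objective the SAP keeps only a logistic model of a symptom score cut at 15 on three volume classes, and drops the protocol's Spearman and chi-square analyses without declaring it; full-scale estimates should be added beside the model.

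*SAP*

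**What the plan says.** Protocol section 14 (Secondary objectives) asks whether low, normal and high ranges of mPV or mTBV on days 1 and 3 are associated with PGA, dyspnea, dizziness and nausea over the following 24–48 hours. It plans logistic regression and then adds: "Associations will be assessed by chi-square interaction tests and by Spearman's correlation coefficient". It gives no numeric limits for the ranges and no cut for the symptoms.

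SAP section 4.3.1 treats the symptoms as levels ("Current level and level within last 24 hours of well-being, dyspnea, dizziness, nausea reported on day 1 and day 3") and lists them again at 24 and 48 hours after each dosing day. SAP section 7.7.1 then counts a symptom as present when its current score exceeds 15, and sets the status classes at below -10%, -10% to +10%, and above +10% of ideal volume. It fits a logistic "model with occurrence of symptoms (PGA, dyspnea, dizziness, nausea) as dependent variable and the categorized measured value (mPVS, mTBVS) as independent variables", adjusted for mean arterial pressure. Neither Spearman's coefficient nor a chi-square test appears for this objective.

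SAP section 8 lists the changes from the protocol. It covers variable selection ("In general, no variable selection will be done in the regression models due to limited sample size"), the use of mPVS and mTBVS to define low, normal and high, the switch from t-tests to Bland-Altman analyses, and the added haemoglobin and cystatin C formulas. It does not mention the loss of Spearman and chi-square or the cut at 15.

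**The concern.** mPVS and mTBVS are continuous percentages, and the symptom scores are numeric enough to carry cut-offs of 15 and 25 in the same SAP section. After both cuts, a status of +11% counts the same as one of +50%, and a score just above 15 counts the same as any higher score. With at most 50 patients per dosing day, that is a heavy loss of information in the one analysis dedicated to this question. Uncommon symptoms may also leave too few events to estimate the class odds ratios.

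PGA is a particular difficulty. A value above 15 counts as a symptom here, while a value below 25 counts as a low-output complication in the next analysis. A score of 20 therefore counts in both. An uncut analysis does not depend on either threshold.

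The trial aims to generate hypotheses. What is at stake is whether it returns usable estimates of this association, or reports none largely because of the scale on which it was analysed.

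**Working it through.** **Inputs from the documents.** N = 50, with no sample size calculation: "We plan to enrol 50 eligible patients. Due to the explorative nature of this phase II study a formal sample size calculation is not possible". Score cut at 15, status cuts at -10% and +10%, mean arterial pressure as covariate (SAP section 7.7.1). There is no power or alpha figure to reproduce.

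**Assumptions.** Two-sided alpha 0.05. Status and score are bivariate normal with correlation r. mPVS has mean +5% and SD 15%. The share of scores above 15 is 20%, 35% or 50%.

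**Class shares.** Low: Φ((-10 - 5)/15) = Φ(-1) = 16%. High: 1 - Φ((10 - 5)/15) = 1 - Φ(0.33) = 37%. Normal: 47%.

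**Spearman on full scales, by formula.** Power ≈ Φ(atanh(r) × √((N - 3)/1.06) - 1.96), with √(47/1.06) = 6.66.
- r = 0.2: Φ(0.203 × 6.66 - 1.96) = Φ(-0.61) = 0.27
- r = 0.3: Φ(0.310 × 6.66 - 1.96) = Φ(0.10) = 0.54
- r = 0.4: Φ(0.424 × 6.66 - 1.96) = Φ(0.86) = 0.81
- r = 0.5: Φ(0.549 × 6.66 - 1.96) = Φ(1.70) = 0.96

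**Planned test, by simulation.** Likelihood-ratio test (2 df) of the three-class logistic model, without the covariate, against Spearman on the same simulated data. Differences carry a Monte Carlo error of a point or two.

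| r | Spearman, full scales | Planned model, 20–50% above 15 | Loss (points) |
|---|---|---|---|
| 0.2 | about 0.27 | about 0.13–0.16 | 11–14 |
| 0.3 | about 0.53 | 0.22–0.28 | 25–31 |
| 0.4 | about 0.79 | 0.34–0.47 | 32–45 |
| 0.5 | about 0.94 | 0.52–0.67 | 27–42 |

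**If the protocol meant Spearman on the three ranges with the uncut score.** Power is 0.44–0.45 at r = 0.3 and 0.70–0.71 at r = 0.4. The loss is then 16–23 points (0.44 - 0.28 to 0.45 - 0.22) and 23–37 points (0.70 - 0.47 to 0.71 - 0.34). At r = 0.2 it is about 7–10 points.

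**Which cut costs what.** A separate simulation adjusted for an independent covariate standing in for mean arterial pressure. At r = 0.4, with equal classes and 30% above 15, Spearman has 0.79, logistic regression on continuous volume 0.62 and the planned model 0.44. Cutting the symptom costs about 17 points and cutting volume about 18. Under that set-up the loss was 24–44 points for r = 0.3–0.5, 20–50% above 15 and classes of 33/33/33% or 20/30/50%. With 10% above 15 or classes of 10/20/70% as well, and r down to 0.2, it ran from about 10 to 87 points.

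**Estimability.** With 20% above 15 there are about 10 events for two class terms plus mean arterial pressure, or 10/3 = 3.3 per coefficient. The low class holds about 0.16 × 50 = 8 patients. At r = 0.3 about 9% of them exceed the cut, so the chance of no event among them is about 0.91^8 = 0.47. Counting all three classes, 51% of simulated trials had a class with all or no events. At 10% above 15 the figure was 81%.

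**A relation that is not linear.** With the score rising with |mPVS| (correlation 0.4, N = 50, 20–50% above 15), the ranking depends on where the population sits:
- mean +5%, SD 15%: three-class model 33–37%, Spearman 22–26%
- mean 0%: 35–36% against 6–7%
- mean +10%, SD 20%: 30–32% against 39–41%

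**The case against.** The strongest reply is that the trial makes no confirmatory claim. SAP section 7.1 says that "all analyses including p values are purely descriptive" and that "this limited number does not allow to address a complex multiple testing problem with adequate power", so a shortfall in power breaks no promise. That stands, and it is why the cost is better read as lost precision and unstable odds ratios. It does not excuse odds ratios that cannot be estimated, or an undeclared departure from the protocol.

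Four stronger readings are tempting, and the documents do not support them.
- A reader might infer that the SAP introduced the classes and the binary model. The objective itself speaks of low, normal and high ranges, and the protocol already says "Logistic regression models will be generated and potentially adjusted for other relevant confounders. Associations will be assessed by chi-square interaction tests". SAP section 8 also declares the status classes.
- A reader might infer that nothing else in the plan relates volume to symptoms. The next two analyses in SAP section 7.7.1 do so, through low-output complications (dizziness, nausea, PGA) and refractoriness to diuretics (failure to improve in PGA and dyspnea). Their outcomes are also binary.
- A reader might take the protocol's Spearman to mean uncut volume. The protocol does not say, so both versions are given above.
- A reader might want Spearman to replace the three-class model. The protocol looks for trouble at both ends of volume, and for a U-shaped relation the three-class model can be clearly better.

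The symptom sheet (Annex D) is not in the text available for this review, so the range and direction of the scales, and any reason for 15, could not be checked.

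**Conclusion.** The point holds as a conditional one. It is certain from the text that Spearman and chi-square were planned, are absent from the SAP for this objective, and are not declared as changes. The SAP's own contribution is that omission and the numeric cut-offs.

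The size rests on an assumed linear relation, N = 50, the assumed mPVS distribution and 20–50% of scores above 15. The loss against full-scale Spearman is then about 11–14 points at correlation 0.2 and 25–45 at 0.3–0.5. Against Spearman on the three ranges it is about 7–10 and 16–37. A reader might be tempted to quote one unconditional figure, or to say a real association is more likely missed than found. The documents fix no correlation, and at 0.5 the planned test has 52–67% power.

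The estimability problem is independent of any power target: about half of trials at 20% above 15 and correlation 0.3. The primary endpoints are unaffected. This is a cheap improvement to one exploratory secondary objective.

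**What to change.** In SAP section 7.7.1, add for this objective:
- Spearman's correlation between continuous mPVS, and separately mTBVS, and each uncut symptom score at 24 and 48 hours, with 95% confidence intervals.
- A linear or ordinal regression of the uncut score on continuous status, adjusted for mean arterial pressure as already planned, with 95% confidence intervals.

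Keep the three-class logistic model alongside. In SAP section 8, list whatever still differs from protocol section 14, including the chi-square tests if they are not restored and the cut at 15, with the reason. State how the two PGA thresholds in section 7.7.1 fit together.

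The cost is SAP wording and a few lines of R on data already collected. The downside is a few more exploratory estimates to report.
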